6 CHIVITT STUDY DESIGN

Each CHIVITT is planned to be conducted with discrete cohorts of Recipients and Donors. The size of each cohort and numbers of Recipients and Donors will vary from cohort to cohort, but the general size of a cohort may consist of up to 20 Recipients and up to 5 Donors per CHIVITT, which would span an approximate 2-week period. The number of Recipients will be determined by each individual's availability and whether their most recent serum antibodies have demonstrated a relative low titer against the influenza virus to be transmitted in the CHIVITT. To maintain the size of the recipient group, we may consider bringing in new recipients during the quarantine study if a significant number of original recipients are infected on the same day. The number of Donors will be determined by the number of participants which are identified with acute symptomatic influenza infection during the time of a CHIVITT cohort's stay.

The CHIVITT studies are anticipated to occur during the peak of local seasonal influenza transmission (e.g., January and February). Timing of the study will be constrained by the necessity to rent the facility for prespecified calendar dates. It is intended that the local seasonal influenza activity will be closely monitored, including the virus subtypes which are predominantly circulating. During the peak of the local seasonal influenza activity, a cohort of Recipients will be contacted to request their willingness to reside up to ~2 weeks on the quarantine research unit for a CHIVITT. The selection of Recipients from the pool of potential Recipients will be partially determined by the demonstration of low antibody titers against the circulating influenza virus, which has been measured in the past year (under the EMIT-2 Recipient Protocol, UMB IRB HP-97730). Potential Recipients will be given some time (\leq one week) to decide whether to participate and they must complete an IRB-approved consent form for the CHIVITT study.

Meanwhile, during the peak of community-wide local seasonal influenza the study team will be attempting to rapidly identify healthy adults with acute and symptomatic influenza infection for consent to participate as Donors in the CHIVITT cohort. It is intended that there could be multiple Donors identified during a ~2-week period; each of these Donor individuals could be introduced into the CHIVITT cohort in an overlapping or sequential fashion, to provide more opportunities for transmission events.

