8.2 Research Laboratory Evaluations

HAI and FRNT Assays

The ability of antibodies to inhibit the interaction of hemagglutinin (HA) protein on the surface of influenza virus with sialic acids on the surface of red blood cells (RBCs) will be examined by hemagglutinin inhibition (HAI) assay performed on serum samples from study participants at the specified collection timepoints. The readout will be the ability of antibodies to inhibit hemagglutination, HAI titers. For H3N2 viruses that have no HA activity, serum antibody will be titred using a focus reduction neutralization test (FRNT) in which the ability of the serum to inhibit the formation of infectious foci in cell culture will be measured. The HAI and FRNT assays are to be performed with deidentified specimens at a collaborating lab ([name], Icahn School of Medicine at Mount Sinai, New York, NY). The virus strain-specific HAI or FRNT titer will be considered the primary method for determining a participant's immunity.

Potential Antibody Assays if funding is available

A brief listing of some of the potential additional antibody assays which may be performed on serum and/or nasal wash specimen includes the following:

- Microneutralization (MN) assay, measures the ability of antibodies to prevent cytopathologic effects in cell cultures infected with influenza viruses.
- Neuraminidase inhibition (NI) assay, measure antibodies that block the enzymatic activity of the neuraminidase protein (NA), a surface glycoprotein which cleaves sialic acid residues.
- Enzyme-linked immunosorbent assay (ELISA), measures binding antibodies against full-length HA, HA-stalk, NA, and other influenza antigens.

- Influenza virus protein microarray, an approach which can measure the “landscape” of serum antibodies by measuring the binding against hundreds of HA and NA proteins simultaneously and spanning multiple virus subtypes and strains.
- Antibody-dependent cellular cytotoxicity (ADCC) assay, functional antibody assay.

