9 OUTCOMES AND DATA ANALYSIS

9.1 Primary Outcome Measure – Attack Rate of Influenza

The SAR of influenza infection will consist of virological confirmation, symptomatic infection, or serological evidence of an influenza infection.

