9.1.3 Serological Confirmation of Influenza Infection

Seroconversion. A positive seroconversion will be defined as achieving ≥ 4 -fold increase in serum HAI titer from baseline. The serological assessment will be performed in batched analyses and will not be available for day-to-day decisions.

Seropositive. A seropositive will be defined as a serum HAI titer of ≥ 40 at 1-month post-CHIVITT. The serological assessment will be performed in batched analyses and will not be available for day-to-day decisions.

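### A 1-month HAI titre of 40 or more can count as influenza infection with no baseline condition, and the serological definition omits the FRNT assay planned for some H3N2 strains

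*Protocol*

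**What the plan says.** Protocol section 9.1 defines the primary outcome: "The SAR of influenza infection will consist of virological confirmation, symptomatic infection, or serological evidence of an influenza infection". The objectives table in section 5 joins the same three limbs with the same "or".

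Section 9.1.3, headed as serological confirmation of infection, then gives two definitions. Seroconversion is a 4-fold or greater "fold increase in serum HAI titer from baseline". For the other: "A seropositive will be defined as a serum HAI titer of" 40 or more at 1 month after the CHIVITT. The second has no baseline condition, and nothing says that both must be met. The section does not say which serum is the baseline.

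On who enters with what antibody, section 6 says that selection of Recipients is "partially determined by the demonstration of low antibody titers against the circulating influenza virus, which has been measured in the past year". Section 4.1 lists no titre limit among the Recipient criteria.

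On the assay, section 8.2 says: "For H3N2 viruses that have no HA activity, serum antibody will be titred using a focus reduction neutralization test (FRNT"). It adds: "The virus strain-specific HAI or FRNT titer will be considered the primary method for determining" immunity. Section 9.1.3 names HAI alone in both definitions.

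**The concern.** A single titre after exposure cannot show that infection happened during the CHIVITT. A Recipient who arrives with a titre of 40, is never infected and leaves with a titre of 40 meets the seropositive definition. Such cases have nothing to do with the exposure conditions. If they are spread evenly over the groups compared, they raise both attack rates, shrink the relative reduction and cost power on the primary endpoint. They would also distort the observed attack rate that section 8.1.2 allows the team to use, from an initial control-only event, to judge the power of later events.

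The second part is a conflict between sections. If the Donor virus is an H3N2 strain with no HA activity, section 8.2 moves to FRNT, but section 9.1.3 has no FRNT criterion. For that strain the serological limb cannot be scored as written.

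**Working it through.** **1. Whom does the seropositive rule add?** Let b be the baseline titre and t the 1-month titre. Seroconversion is t/b ≥ 4 and seropositive is t ≥ 40. A person added by the second rule alone has t ≥ 40 and t/b < 4, so b > t/4 ≥ 10. Assuming two-fold dilutions with titres below 10 set to 5, the baseline is 20 or higher. Examples are 20 to 40, 40 to 40, 40 to 80 and 80 to 80. A change from 5 or 10 to 40 is already a seroconversion. So every serological case added is unchanged or falling antibody, or a single two-fold step, which the seroconversion rule does not itself accept.

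**2. Reproducing the plan's power.** Inputs from section 9.2: attack rate 25%, reductions of 79% (n = 54) and 76% (n = 63), one-sided 5%, stated power 84% for each. The control group size is not stated, so equal groups are assumed.

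With p1 = 0.25, p2 = 0.25 × (1 − 0.79) = 0.0525, mean p̄ = 0.15125 and a continuity correction:

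Power = Φ{[(p1 − p2) − 1/n − 1.645 × √(2p̄(1 − p̄)/n)] / √[(p1(1 − p1) + p2(1 − p2))/n]}

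= Φ{[0.1975 − 0.0185 − 0.1134] / 0.0663} = 83.9%.

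This matches the stated 84%. For n = 63, p2 = 0.06 and the same formula gives 86.3%. The two-sided pooled formula without correction gives 84.7% there and 82.7% at n = 54. No single one-sided variant tried gives 84% for both sizes, so both formulas are shown for n = 63.

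**3. Adding false positives.** Let f be the share of uninfected Recipients with HAI ≥ 40 at 1 month, taken as equal in both groups. Observed rate = p + f(1 − p). At f = 5%: 0.25 + 0.05 × 0.75 = 0.2875, and 0.0525 + 0.05 × 0.9475 = 0.0999. The apparent reduction is 1 − 0.0999/0.2875 = 65%. The protocol gives no titre distribution, so every f is an assumption.

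n = 54 per group, true reduction 79%:

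| f | Control | Intervention | Apparent reduction | Power (one-sided, corrected) |
|---|---|---|---|---|
| 0% | 25.0% | 5.25% | 79% | 83.9% |
| 2% | 26.5% | 7.1% | 73% | 79.2% |
| 5% | 28.8% | 10.0% | 65% | 72.4% |
| 10% | 32.5% | 14.7% | 55% | 62.2% |
| 20% | 40.0% | 24.2% | 40% | 46.3% |

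n = 63 per group, true reduction 76% (hand hygiene and face shield):

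| f | Control | Intervention | Apparent reduction | Power (one-sided, corrected) | Power (two-sided, pooled) |
|---|---|---|---|---|---|
| 0% | 25.0% | 6.0% | 76% | 86.3% | 84.7% |
| 2% | 26.5% | 7.9% | 70% | 82.0% | 79.8% |
| 5% | 28.8% | 10.7% | 63% | 75.7% | 72.6% |
| 10% | 32.5% | 15.4% | 53% | 65.7% | 61.6% |
| 20% | 40.0% | 24.8% | 38% | 49.5% | 44.5% |

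**4. The assay conflict.** No arithmetic applies. Section 8.2 uses HAI, or FRNT for H3N2 viruses without HA activity. Section 8.1.1 draws admission blood for both assays. Section 9.1.3 offers a criterion for HAI only. The limb is therefore undefined for the strains that section 8.2 singles out.

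**The case against.** *The rule is not explicit.* Section 9.1.3 does not say that a seropositive result alone makes a case, and how the components combine might be left to an analysis plan. That is fair as to wording. But the heading of 9.1.3 and the "or" in 9.1 make the stand-alone reading the natural one, and this is the protocol's own definition of its primary outcome.

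*Recipients are chosen for low antibody.* Section 2.3.1 says that the separate Recipient Protocol screens for adults lacking antibody likely to protect them, and that protocol, not at hand, may set a titre cut-off or a vaccination rule. This stands as a limit on size: f may be small, and 20% sits poorly with such selection. It does not remove the problem. Section 6 makes selection only partly dependent on titre, the titre may be up to a year old, and no cut-off appears here.

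*The power model is not the design.* Also fair. Section 9.3 plans a GEE clustered by cohort, and from the second year section 6.1 alternates air hygiene within cohorts. The tables illustrate dilution; they do not predict the trial's power.

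*False positives fall equally everywhere.* A reader might infer this for every comparison. Randomisation supports it, in expectation, only for Intervention versus Control Recipients. Recipients are not randomised to air hygiene, so equal f is purely an assumption in the n = 54 table.

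*H3N2 seasons lose their serological cases.* A reader might infer this too, but section 8.2 limits FRNT to H3N2 viruses without HA activity. Even then an infection leaves the composite only if the molecular testing (daily after Donor exposure, section 8.1.3) and the symptomatic limb also miss it.

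*The baseline is obvious.* Admission blood is drawn for these assays and is the natural choice. The text should still say so, because the screening serum is a second candidate.

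**Conclusion.** The point holds. Read with section 9.1, the seropositive definition in 9.1.3 adds to the serological limb only people without a 4-fold rise, so it can count pre-existing antibody as infection. For Intervention versus Control Recipients the expected consequence is dilution toward no effect and lost power, not bias in favour of the intervention.

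The size is not known. It depends on f, which the documents do not give. Over an assumed 2 to 20%, the apparent reduction falls from 79% to between 73% and 40%, and illustrative power from 84% to between about 79% and 46%. These figures assume two equal, independent groups of 54, a one-sided 5% test with continuity correction, and equal f in both groups. A reader might infer that a large loss has been shown; it has not, and at f = 2% the loss is about 5 points of power.

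The omission of FRNT is a plain conflict with section 8.2, confined to strains without HA activity and to infections that the other two limbs miss.

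**What to change.** In section 9.1.3, define serological infection as a 4-fold or greater rise from the CHIVITT admission serum to the 1-month serum, against the Donor strain, by HAI, or by FRNT where the strain has no HA activity. Keep HAI of 40 or more at 1 month as a descriptive measure that does not make a Recipient a case.

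The cost is a few sentences. Admission blood for both assays (section 8.1.1) and 1-month blood (section 8.1.8) are already collected, and section 8.2 already plans both assays. Because serology is batched and plays no part in daily decisions, study conduct does not change. A true infection with less than a 4-fold rise would then have to be caught by virology or symptoms, but the present rule cannot tell such a case from unchanged antibody.

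A reader might also want Recipients vaccinated between the two sera judged on virology alone. That should not be added: it would drop the symptomatic limb for them without need, and would require a vaccination history that the 1-month visit does not list.

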9.2 Sample Size Considerations

We estimate effect sizes of interest based on an expected SAR of 25% and two alternate hypotheses that: a) long-range aerosol transmission accounts for 75% of transmission and b) contact, fomite, and spray-borne transmission account for 60% transmission. These hypotheses are essentially attributable fractions, not the expected effect size of the interventions. The interventions, unfortunately, cannot cleanly block one mode without impacting transmission via other modes. Therefore, we derived the estimated effect sizes for the interventions by analysis of planned interventions and their impact on each mode of transmission. It is assumed that hand hygiene and face shield is 100% effective for contact and spray-borne transmission and the effectiveness for short-range aerosols is based on the work of Lindsley⁵ and Bischoff⁶. The air hygiene (ventilation, filtration, and germicidal UV light) intervention will be designed to be 100% effective against long-range aerosol transmission using a validated computational model of these systems, to be developed by Research Project 2 of the EMIT-2 U19 Project, to achieve the equivalent of > 60 ACH. However, air hygiene interventions are relatively less effective against short-range aerosol transmission.

Because of incomplete blockage of aerosol transmission by air sanitation and partial blockage of short-range transmission by the face shields, we assume marginal effect size of 79% reduction in the observed SAR. To compute power, we use one-sided alternatives because we do not expect that either intervention is capable of increasing transmission. Given a sample size of 54 in an intervention group, we will have 84% power to detect the intervention effect with an alpha level of 5%.

For power to detect an effect of contact, fomite, and spray-borne transmission, we assume a marginal effect size of 76% reduction in observed SAR. Given a sample size of 63 in an intervention group, we will have 84% power to reject the null hypothesis of no effect with the hand hygiene and face shield.

9.3 Analysis Plan

We will plan to analyze the binary outcome (SAR of influenza infection) using a generalized estimating equation (GEE) with a logistic link function. Individuals sharing a CHIVITT cohort will be considered as a cluster and the dependence will be adjusted by the working correlation in the GEE model. The effect of the interventions will be treated as independent, and the analysis will be controlled for sex, race-ethnicity, and age \geq or < 30 years. We will examine sex as a biological variable for a main effect on infection risk but will not have sufficient power to perform subgroup analysis. R markdown and reproducible statistical analysis will be applied to ensure maximal reproducibility of the data analysis.

Continuous data will be transformed (e.g., Box-Cox transformation) to meet the normality assumption in the analysis. To compare proportions among unpaired samples, we will use logistic regression and adjust covariates as needed. For paired samples, we will use the conditional logistic regression. To examine the group effect on the continuous effect, we will use the general linear model. To test for a trend across

groups, we will use the chi-squared test for trend to compare proportions or Cuzick's test for trend to compare continuous data. Spearman correlation tests will be used to assess correlations between non-binary ordinal variables. The association of immunological measures and other covariates on the risk of infection will be examined using generalized estimating equations (GEE) with a Poisson distribution and robust standard errors to overcome the potential overdispersion. Principal components analysis (PCA) will be used to assess the extent to which variables can be summarized using a smaller number of components. The potential effects of age and sex will be examined in all multivariable models.

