Title: Evaluating Modes of Influenza Transmission through the conduct of controlled human influenza virus infection transmission trials (CHIVITTs)

Population: up to 200 persons, among which 175 may be Recipients aged 18 through 49 and 25 may be Donors aged 18 through 59 years

Number of Sites: at least 2 (University of Maryland, Baltimore and University of Maryland, College Park)

Study Duration: approximately 5 years

Subject Duration: Up to approximately 2 months.

Primary Objective:

- The primary objective of EMIT-2 is to use a randomized controlled trial (RCT) design to implement interventions which are known to reduce inhalation (airborne) transmission, so that the contribution of transmission by route of aerosols for influenza may be identified.

Primary Endpoint:

- Secondary attack rate (SAR) of influenza in Recipients participating in RCTs of air sanitation-ventilation-filtration and contact-fomite interventions, so called controlled human influenza virus infection transmission trials (CHIVITTs).

Secondary Objectives:

- To measure influenza viral parameters in both Donors and Recipients, including the incidence, duration, and quantity of virus shedding
- To measure influenza illness parameters in both Donors and Recipients, in order to assess the impact of aerosol exposure to influenza virus on disease severity
- To evaluate the role of serologic and mucosal antibody levels on influenza transmission, susceptibility, and immunologic response to infection
- To estimate the infective dose of influenza via aerosol inhalation, through measurement and modeling of aerosol size, virus number per aerosol particle, deposition and environmental dispersion characteristics, and rate of shedding

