6.1 General Outline of Activities During Each CHIVITT Cohort

The CHIVITT is to be conducted as a randomized, open, controlled study. Recipient participants for each cohort will enter the study hotel quarantine facility and be housed in individual hotel rooms. After a two-day run-in period to ensure that Recipients are free of preexisting respiratory infections *Exposure Events* will be held in a specially prepared event room.

Recipient participants of each cohort will be randomized to an intervention group or no intervention (Control Recipients, CR). Before entering their first *Exposure Event* each Intervention Recipients (IR) will be trained on how to comply with the intervention. IRs will be required to wear a lightweight plastic face shield, comply with hand hygiene (i.e., using a hand sanitization product every 15 minutes, plus periodic hand washing with soap and water), and avoid face touching during each planned *exposure event*. The face shield may only be removed after leaving the exposure room to go to the bathroom, for other short comfort breaks, and at mealtimes. In these instances, hand hygiene will be used after removing or replacing the face shield; and Donors will not be present. Hand washing with soap and water will be required before meals. IR will be separated from Donors by more than 6 feet during meals. The exposure room will be supervised by a trained member of the study staff who will monitor to ensure that Intervention Recipients wear the face shield continuously, are separated from Donors at meals, and do not touch their faces. Small sticks (e.g., coffee stirrers) will be provided to allow IRs to scratch their faces.

Exposure events are to occur as controlled (prescribed) activities within the exposure room. Exposure events will extend for up to 15 hours per day when Donors are available and able to participate (e.g., 15 hours 8am to 11pm). Each Recipient will participate in up to 60 hours of *Exposure Events* (e.g., 4 days at 15 hours/day) which may be spread over up to 9 or 10 days. During each *Exposure Event* multiple 1-3 hour group activities will be planned and supervised by trained members of the study staff. The group activities are intended to be entertaining and may consist of participating in a card game, board game, foosball game, karaoke, or other group activity which facilitates crowding, loud talking, etc. for potential influenza transmission.

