Meanwhile, the exposure room environment will be regulated to control room temperature, humidity, and air hygiene for each CHIVITT. The overarching design of the EMIT-2 program is the evaluation of the contribution of aerosol inhalation to influenza transmission. In order to evaluate the effect of aerosol inhalation, we may alternate the air quality and cleaning between high and low air hygiene conditions during each quarantine cohort with a wash-out period (for example 2 days). High air hygiene conditions will be those where ventilation, filtration, and/or germicidal UV will achieve effective air exchanges of ≥ 10 air changes per hour (eACH), or >10 liters/second/person, or a mean target CO₂ concentration of ≤ 200 parts per million (ppm) above the outdoor concentration (if high air hygiene is achieved with ventilation alone). Low air hygiene conditions will be those where effective air exchanges will be ≤ 0.7 ACH or <1 liter/second/person (similar to an unventilated dorm room at the University of Maryland College Park), or a mean target CO₂ concentration of $\geq 2,500$ ppm (similar to a poorly ventilated public-school classroom), or as low as achievable while controlling temperature in a comfortable range and relative humidity $<40\%$. It is intended that the first CHIVITT (Year 1) will be performed with the low air hygiene, ventilation, filtration, and no germicidal UV conditions so that we can determine the attack rate of influenza under

the circumstances which will most facilitate inhalation exposure and influenza transmission. In subsequent years, the air hygiene conditions will be alternated within each CHIVITT cohort.

Within the exposure room, digital cameras will be mounted for photography and video recording of the *exposure events*. The photos and video information are used to monitor and characterize the direction of exhaled breath, duration and proximity of persons from each other, and other positional information which will be needed to develop the analytical models of aerosol transmission. Although the content of conversations is not the intent of the recordings, some audio data may be analyzed for “loudness” and audible coughs and sneezes, as a proxy for periods during which higher exhaled breaths may be generated. In some CHIVITTS we may employ newer technologies, such as wearable biosensors with geo-positional data collection to allow for the investigators to collect data on minute respiratory rate, heart rate, and proximity.

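### The primary model cuts age at 30 without a reason; age in years costs the same single coefficient and keeps information that the cut discards

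*Protocol*

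**What the plan says.** Section 9.3 analyses the binary infection outcome "using a generalized estimating equation (GEE) with a logistic link function", with cohort as the cluster. It states that "the analysis will be controlled for sex, race-ethnicity, and age", and the sentence then sets age at a two-level split: "or < 30 years. We will examine sex as a biological variable for a main effect on infection risk". No reason for 30 is given, and no analysis with age in years is named.

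The Protocol Summary says that "175 may be Recipients aged 18 through 49", so the split groups ages 18 to 29 and ages 30 to 49.

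The last sentence of 9.3 adds: "The potential effects of age and sex will be examined in all multivariable models". It does not say in what form age enters those models.

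The two interventions are allocated differently. For face shield and hand hygiene, section 6.1 says "Recipient participants of each cohort will be randomized to an intervention group or no intervention". For air hygiene, the same section plans Year 1 at low hygiene only, and then: "In subsequent years, the air hygiene conditions will be alternated within each CHIVITT cohort". No individual randomisation to the air condition is described.

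**The concern.** Eligibility rests on age, so age in years is available for every Recipient. The split treats an 18-year-old like a 29-year-old and a 29-year-old unlike a 30-year-old. Splitting a continuous covariate can be defended if it saves parameters or matches a known step in risk. Here it saves none, and the protocol claims no step.

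Two things could be at stake: precision, because a covariate measured coarsely explains less of the outcome; and residual confounding, wherever age differs between the groups being compared. The second arises by chance only in the randomised contrast. It could arise systematically in the air hygiene contrast, because the Recipients of Year 1 contribute low-hygiene exposure only.

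**Working it through.** The protocol gives no figure for age information or age confounding, so there is none to reproduce.

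**Inputs from the protocol.** Recipient ages 18 to 49 (Summary); cut at 30 (9.3); control attack rate 25%, and a 76% reduction with 63 in the face shield and hand hygiene group (9.2).

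**Assumed inputs.** Age distribution, odds ratio per 10 years of age, and 1:1 allocation. None of these is stated.

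**1. Parameter count.** Two-level age: one coefficient. Linear age: one coefficient. Saving: none.

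**2. Share of age variance kept by the cut.** This is the squared correlation R² of age with the indicator for 30 or older. For flat ages it equals 3p(1−p), where p is the share under 30. With ages running from 18 up to the 50th birthday, p = 12/32 = 0.375 and R² = 3 × 0.375 × 0.625 = 0.70, so about 30% is lost. Other assumed shapes on 18 to 49 give:

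| Assumed shape | Loss |
|---|---|
| Student-heavy mixture (30–80% aged 18–22, rest flat) | 16–20% |
| Moderately young-skewed | 27–31% |
| Flat | 30% |
| Bell-shaped | 32–46% |
| Strongly young-skewed | 36–53% |

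**3. Randomised contrast: power.** Simulated logistic models without clustering, 63 per arm, attack rates of 25% and 25% × (1 − 0.76) = 6% at mid-range age, flat ages, one-sided 5% test. Only the difference between codings matters here; the levels are not a check of the plan's 84%.

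| Odds ratio per 10 years | Cut at 30 | Age in years |
|---|---|---|
| 1 | 93.9% | 94.1% |
| 1.5 | 92.7% | 93.0% |
| 2 | 92.7% | 93.1% |
| 3 | 93.8% | 95.7% |

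**4. Randomised contrast: chance imbalance.** The difference in mean age between two arms of 63 has a standard deviation of √(2/63) = 0.18 SD of age. With an age SD of 9.24 years (flat) and an odds ratio of 1.5 per 10 years, this is 0.18 × 9.24 × ln(1.5)/10 = 0.07 log odds unadjusted. After the cut about 0.07 × 0.30 = 0.02 remains, against a standard error of about 0.65 for the intervention effect.

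**5. Non-randomised contrast: bias.** Simulation with no true effect and a deliberately large age difference between conditions (about half an SD):

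| Age effect | No age term | Cut at 30 | Age in years |
|---|---|---|---|
| Linear, odds ratio 1.5 per 10 years | 0.166 | 0.058 | −0.003 |
| Linear, odds ratio 2 per 10 years | 0.275 | 0.102 | −0.003 |
| Step at 30, smaller | 0.113 | −0.012 | −0.014 |
| Step at 30, larger | 0.195 | −0.007 | −0.006 |

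With a linear effect, the cut leaves 0.058/0.166 = 35% or 0.102/0.275 = 37% of the bias, near the 30% that 1 − R² gives to first order. With a true step at 30 it leaves essentially none. Each entry averages 8 runs with a standard error of about 0.03 each, so values within about 0.01 of zero are simulation noise.

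**The case against.** The strongest reply is that a pre-specified two-level adjustment covariate is not an error, and that a linear term is itself a shape assumption that nobody has verified. Both statements are true. The near-zero bias with age in years under a linear effect is partly built in, because the data were generated that way. It is also true that no figure in the protocol shows an age imbalance between air conditions. Once conditions alternate within a cohort, the same Recipients can meet both, which limits the imbalance. What the reply does not supply is any reason for 30, or any saving that offsets the lost information.

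Three stronger readings are tempting, and the document does not support them.

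- A reader might infer that the 30-year split also governs the models relating antibody measures to infection, and so leaves confounding there. Section 9.3 ties the split to the primary logistic GEE only. The antibody models are separate Poisson GEEs for which no form of age is stated, and leaving that open is not a fault of the protocol.
- A reader might infer that Recipients are mostly young people recruited around campuses, so that the group aged 30 or older could contain no infections and the age coefficient would not be estimable. Campus recruitment is described in sections 2.3.2 and 3.1 for Donors. Recipients come from a separate screening protocol (sections 2.3.1 and 4), and their age mix is not given here.
- A reader might take a single percentage as the loss. Any such figure depends on the assumed age distribution, as the 16% to 53% range shows.

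**Conclusion.** The point holds as a minor improvement to stated protocol text. The cut at 30 is fixed without a reason, saves no coefficient, and loses about 30% of the age variance if ages are flat (16% to 53% across the other shapes tried).

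For the randomised face shield and hand hygiene contrast the effect is negligible: about 0 to 2 power points, and a residual chance imbalance of about 0.02 log odds against a standard error of about 0.65. It does not threaten that result.

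For air hygiene the case is slightly stronger. About a third of any age bias would remain after the cut, on two conditions that the protocol neither confirms nor excludes: that age differs between low- and high-hygiene exposure, and that risk changes roughly linearly with age. If risk steps at 30, the cut leaves almost nothing behind.

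**What to change.** In section 9.3, replace the two-level age term in the primary GEE by age in years as one linear term. State that the same form is used wherever age enters the other multivariable models. Keep the under-30 and 30-or-older grouping for descriptive tables.

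The cost is a wording change: no new data and no extra parameter. The small downside is the assumption of linearity on the logit scale. The change is best made before outcomes are analysed, so that the form of age cannot be chosen in the light of the results.
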